in the current FDA-approved product labeling for that device (i.e., for an “off-label” indication)?

* No

- 2.2.2.1.1 List each of the devices being evaluated for an “off-label” indication. Specify for each listed device the corresponding Investigational Device Exemption (IDE) number for this device/research study; or provide a justification for why you feel that this device and its “off-label” use, as proposed in this research study (i.e., to include potential failure of the device) constitute a non-significant risk to the involved research subjects.

*

| Device | IDE # | Non-significant risk justification |
|--------|-------|------------------------------------|
|--------|-------|------------------------------------|

There are no items to display

[reviewer notes-]

Section 2 - Research Design and Methods

- 2.3 Summarize the general classification (e.g., descriptive, experimental) and methodological design (e.g., observational, cross-sectional, longitudinal, randomized, open-label single-blind, double-blind, placebo-controlled, active treatment controlled, parallel arm, cross-over arm) of the proposed research study, as applicable.

Prospective, Randomized, Non-blinded, Surgical outcomes, Pilot study assessing clinical outcomes following fat grafting for pain at amputation sites (with and without adipose stem cell enrichment).

- 2.3.1 Does this research study involve a placebo-controlled arm?

* No

[reviewer notes-]

Section 2 - Research Design and Methods

- 2.4 Will any research subjects be withdrawn from known effective therapy for the purpose of participating in this research study?

Section: Section 2 - Research Design and Methods

* No

- 2.4.1 Provide a justification for discontinuing subjects from known effective therapy for the purpose of study participation.
- 2.4.2 Describe the risks to subjects associated with discontinuing them from known effective therapy for the purpose of study participation.

[reviewer notes-]

Section 2 - Research Design and Methods

- 2.5 Will screening procedures (i.e., procedures to determine research subject eligibility) be performed specifically for the purpose of this research study?

* Yes

- 2.5.1 List the screening procedures that will be performed for the purpose of this research study. Do NOT include the inclusion/exclusion criteria in this section as they will be addressed in section 3; questions 3.13 and 3.14.

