2.15.3 Will biological specimens be stored without identifiers or linkage codes? *

[reviewer notes-]

Section 2 - Research Design and Methods

2.16 Will research participants be asked to provide information about their family members or acquaintances?

* No

2.16.1 Describe what information about the third party will be obtained from the participant:

2.16.2 If the information about the third party is of a private nature, can the identity of the third party be readily ascertained or associated with this information?

*

Describe the private information that will be collected and recorded about the third party:

[reviewer notes-]

Section 2 - Research Design and Methods

Section: Section 2 - Research Design and Methods

2.17

What are the main outcome variables that will be evaluated in this study?

Primary outcomes: Improvement of pain at the amputation site, improved ability to tolerate a prosthesis, and generation of a stable volume of adipose tissue at the amputation site (as measured by clinical assessment by rehabilitation sciences and prosthetics team, quality of life measures, and high resolution imaging). This will be compared between the standard fat grafting group (n=15) and the adipose cell enriched fat grafting group (n=15). Secondary outcomes: Local and systemic complications resulting from fat graft procedure (infection, fat necrosis, hematoma, seroma); basic assays of adipose cell behavior to elucidate the functional properties of adipose cells used for grafting, with correlation to outcomes.

2.18

Describe the statistical approaches that will be used to analyze the study data.

* Addressed below:

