Pain and Serial computed tomography imaging will be performed and measured as parametric data sets before fat grafting and afterwards at various time points using a paired t-test model. Repeated measures analysis of variance will be used to evaluate change over time in all outcome measures. Using standard conventions of alpha=0.05 and beta=0.8, an enrollment of thirty patients may provide sufficient power to detect a Cohen's effect size of about 0.9 which is anticipated to be adequate for detecting clinically meaningful differences in the volume of soft tissue. A composite functional score will be constructed from the prosthetics and occupational therapy evaluations and compared between study groups. The details of this analysis, including which evaluations will be included in the score and relative weight, can be best determined as the study progresses and initial data sets are acquired. Additionally, each assessment score from the specific tests will also be considered individually for comparison.

[reviewer notes-]

Section 2 - Research Design and Methods

2.19

Will this research be conducted in (a) a foreign country and/or (b) at a site (e.g., Navajo Nation) where the cultural background of the subject population differs substantially from that of Pittsburgh and its surrounding communities?* No

Note that copies of training records, licenses, certificates should be maintained in the study regulatory binder and are subject to audit by the Research Conduct and Compliance Office (RCCO).

Section: Section 2 - Research Design and Methods

In addition, individuals planning to conduct human subject research outside the United States must complete an optional module on the CITI training website: International Studies. Click [here](#) to access the instruction sheet for accessing optional CITI modules.

- 2.19.1 Address the following for each of the foreign/culturally different sites where this research will be conducted:
- Name of site
 - Name of authorized individual (e.g., IRB Chair) from the local IRB or other human subject protections entity that is responsible for the review and approval of the project; upload approval letter with an English translation, if applicable
 - Name and qualifications of the site collaborator responsible for the conduct of the research (e.g., site PI)
 - The anticipated number of subjects that will be enrolled at that site
 - If Federally funded, provide the Federalwide Assurance number (FWA) assigned to the site *

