All participants who are women of child bearing potential will receive a urine pregnancy dip test at screening and prior to any CT scans and surgical procedure. Subjects who are WOCBP during participation in this clinical trial will be counseled on the risks of pregnancy and importance of avoiding pregnancy while enrolled in this study; pregnancy will result in their removal from the clinical trial.

- 5.4.3 Describe the measures to prevent pregnancy, and their required duration of use, that will be discussed with women of child-bearing potential during and following exposure to research procedures:

All participants who are women of child bearing potential will receive a urine pregnancy dip test at screening and prior to any CT scans and surgical procedure. Furthermore, patients will be counseled on the risks of pregnancy and importance of avoiding pregnancy while enrolled in this study and that pregnancy will result in their removal from the clinical trial

[reviewer notes-]

Section 5 - Potential Risks and Benefits of Study Participation

Section: Section 5 - Potential Risks and Benefits

- 5.5 Do any of the research procedures pose a potential risk of causing genetic mutations that could lead to birth defects?* No

5.5.1 List the research procedures that pose a potential risk of genetic mutations/birth defects:

- 5.5.2 Describe the measures to prevent pregnancy, and their required duration of use, in female subjects and female partners of male subjects during and following exposure to research procedures:

[reviewer notes-]

Section 5 - Potential Risks and Benefits of Study Participation

- 5.6 Are there any alternative procedures or courses of treatment which may be of benefit to the subject if they choose not to participate in this study?* Yes - Describe below:

If Yes, describe in detail: Alternative treatments include prosthetic implants and standard surgical flap reconstruction/revision surgery.

[reviewer notes-]

Section 5 - Potential Risks and Benefits of Study Participation

- 5.7 Describe the specific endpoints (e.g., adverse reactions/events, failure to demonstrate effectiveness, disease progression) or other circumstances (e.g., subject's failure to follow study procedures) that will result in discontinuing a subject's participation?* Describe below:

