Development of complications (e.g., adverse reactions/events, failure to demonstrate effectiveness, disease progression and severe infection at the surgery site) or other circumstances (e.g., subject's failure to follow study procedures, noncompliance of all research visits) that obscure the ability to evaluate the results of the implant will result in discontinuing a subject's participation. All data regarding complications will be captured and adverse event reporting will be conducted through all the appropriate and required regulatory channels inclusive of any and all treatment required and medical course following complication. In every case in which it is possible to do functional evaluation, regardless of complications, the intended outcomes will be measured.

[reviewer notes-]

Section 5 - Potential Risks and Benefits of Study Participation

5.8 Will any individuals other than the investigators/research staff involved in the conduct of this research study and authorized representatives of the University Research Conduct and Compliance Office (RCCO) be permitted access to research data/documents (including medical record information) associated with the conduct of this research study?* Yes

5.8.1 Identify the 'external' persons or entity who may have access to research data/documents and the purpose of this access:

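### Section 5.7 does not say whether outcome visits continue after lack of effect or a complication, so data can go missing because of the primary outcome, and section 2.18 has no rule for missing visits

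*Combined protocol and SAP*

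**What the plan says.** Section 5.7 describes what ends a subject's participation. It opens with "Development of complications (e.g., adverse reactions/events, failure to demonstrate effectiveness, disease progression and severe infection at the surgery site", adds other circumstances such as not following study procedures or missing research visits, and limits both to those "that obscure the ability to evaluate the results of the implant will result in discontinuing a subject's participation". It says that data on complications will be captured, and closes: "In every case in which it is possible to do functional evaluation, regardless of complications, the intended outcomes will be measured".

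Section 2.17 lists "Primary outcomes: Improvement of pain at the amputation site, improved ability to tolerate a prosthesis, and generation of a stable volume of adipose tissue", to be compared between the two arms of 15. Section 2.3 calls the trial "Prospective, Randomized, Non-blinded, Surgical outcomes, Pilot study".

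Section 2.7 schedules a pain assessment at every post-operative visit to POV6 (two years). CT or MRI is due at POV4, POV5 and POV6 (months 6, 12 and 24).

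Section 2.18 says that pain and CT data will be "measured as parametric data sets before fat grafting and afterwards at various time points using a paired t-test model", and that "Repeated measures analysis of variance will be used to evaluate change over time in all outcome measures". It gives no analysis set, no rule for a missing visit and no sensitivity analysis. Section 5.16 keeps data recorded before a withdrawal in use, but does not say how they enter the analysis.

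**The concern.** Lack of effect is itself a result on the primary outcomes. If it can end participation, whether a later visit exists can depend on how the patient is doing. Section 5.7 does not define *obscure* or name who judges it. It does not say whether a discontinued patient keeps the visits to POV6. Its last sentence applies only where functional evaluation is possible, and that can itself depend on outcome: in section 2.7 the six-minute walk is skipped for a patient who cannot functionally ambulate with the prosthesis. Pain and imaging follow-up of patients who cannot be functionally evaluated is not addressed.

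A paired t-test at a later visit uses only patients who have that visit, and repeated-measures ANOVA in its usual form uses only complete patients. If patients seen to fail leave before later visits, those who remain look improved in pain even when nothing has changed. Between arms, the worse arm loses more of its bad results, so a true benefit of cell enrichment is diluted.

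**Working it through.** **The plan's own figure.** Section 2.18 gives 30 patients, alpha 0.05, *beta* 0.8 (read as power 0.80) and Cohen's d of about 0.9. With 15 per arm the noncentrality is 0.9 / √(2/15) = 2.465.
- Normal approximation: Φ(2.465 − 1.645) = 79% one-sided; Φ(2.465 − 1.960) = 69% two-sided.
- Noncentral t, 28 df: 78% one-sided; 66% two-sided.

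The stated figure fits a one-sided test, but section 2.18 gives no sidedness. The between-arm results below are two-sided.

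**Assumptions.** The documents give no loss rate and no visit-to-visit correlation, so both are varied. Changes are normal with SD 1. A is the change at the visit where failure is recorded, B is the change at a later visit, and r is their correlation.

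**Before/after pain test.** There are 30 patients and no true change. The k worst on A lose B, and a two-sided 5% paired t-test is run on the remaining B values. Bias is r × (mean of the best 30 − k values of A). That mean is 0.186 SD for k = 3 and 0.338 SD for k = 6. Rates of significant false improvement are simulated (nominal 2.5%).

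| r | bias, 3 lost | false improvement | bias, 6 lost | false improvement |
|---|---|---|---|---|
| 0.3 | 0.06 SD | 4.8% | 0.10 SD | 7.3% |
| 0.5 | 0.09 SD | 7.3% | 0.17 SD | 13.8% |
| 0.7 | 0.13 SD | 11.4% | 0.24 SD | 24.9% |
| 1 (upper bound) | 0.19 SD | 22% | 0.34 SD | 53% |

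The zero-change null suits pain. It is not applied to graft volume, which the procedure itself adds.

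**Using the visits already recorded.** Estimate the mean of B as (mean B in those observed) + slope × (mean A in all 30 − mean A in those observed). With loss driven by A alone and r = 0.3-0.7, bias is within 0.001 SD and false improvement is 2.4-3.0%. If loss depends equally on A and the unseen B (r = 0.5; 3 or 6 lost), complete-case bias is 0.16 or 0.29 SD, and 0.10 or 0.21 SD remains after this adjustment.

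**Between arms.** There are 15 per arm. Any patient whose A falls below one common threshold, set at the 10th or 20th percentile of the standard arm, loses B.
- No true difference: bias within 0.005 SD, rejection 4.9-5.2%.
- True difference 0.9 SD: mean loss is 1.5 v 0.2 patients (10th percentile) or 3.0 v 0.6 (20th percentile).

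| r | observed difference, 10% / 20% | two-sided power, 10% / 20% |
|---|---|---|
| no loss | 0.90 SD | 66% |
| 0.3 | 0.85 / 0.82 SD | 59% / 53% |
| 0.5 | 0.82 / 0.77 SD | 57% / 50% |
| 0.7 | 0.79 / 0.72 SD | 56% / 48% |
| 1 (extreme) | 0.74 / 0.64 SD | 56% / 46% |

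Smaller numbers alone would give 63% (13.5 v 14.8 patients) or 60% (12 v 14.4). The rest of the fall comes from dilution. With loss driven by A, the all-available-visits estimate is 0.90 SD for r = 0.3-0.7.

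**The case against.** The strongest defence is section 5.7 itself. Lack of effect is ordinarily a result, not something that hides one, so it would seldom meet the *obscure* condition. The section lists it as a complication, and the last sentence says that complications do not stop measurement. The trigger also repeats the form's own prompt, "Describe the specific endpoints (e.g., adverse reactions/events, failure to demonstrate effectiveness, disease progression". This stands as far as it goes: a consistent reading exists and is the likely one. It does not settle follow-up after discontinuation, or cases where functional evaluation is not possible. The gap in section 2.18 remains however section 5.7 is read.

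The main comparison in section 2.17 is between arms, where a common threshold leaves the null intact. The inflated rate belongs to an uncontrolled before/after test in an unblinded pilot, which could not separate graft effect from expectation even with complete data. That limits the consequence but does not remove the dilution.

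Three stronger readings are not supported:
- *That the plan will drop non-responders.* The trigger is conditional and the last sentence points the other way. Nothing suggests that 3 or 6 patients would be lost.
- *That the arm comparison is biased towards enrichment.* The trial is not blinded, but section 5.7 does not say who judges. A threshold applied differently by arm was not modelled.
- *That section 5.6 shows revision surgery during follow-up.* It lists alternatives for people who do not take part. Only section 1.1 bears on this, in saying that more invasive procedures are not precluded later.

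The separate IDE application listed at CS10.1 is not among the documents and could hold a rule. This point concerns sections 5.7 and 2.18 as they stand.

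**Conclusion.** The point holds in a limited form. Section 5.7 leaves outcome follow-up after lack of effect or a complication unsettled, and section 2.18 has no method for the visits that could be lost. Outcome-dependent missing data are possible, not certain. The before/after pain test is most exposed: about 5-11% false improvement with 3 lost, or 7-25% with 6, against 2.5%. Between arms the effect is dilution. At correlation 0.5, 0.9 SD becomes about 0.82 or 0.77 SD, and two-sided power falls from 66% to 57% or 50% (one-sided, no-loss power is about 78%). All these sizes rest on assumed loss counts and correlations.

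A reader might infer that an analysis of all recorded visits cures the problem. It does so only when loss depends on recorded data, so a sensitivity analysis is still needed. With 30 patients a few lost failures matter and the change is cheap, so it should be made.

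**What to change.** **Section 5.7.** Reconcile the sentences and define *obscure*, so that lack of effect or a complication does not by itself end collection of the pain, imaging and function data already planned to POV6. Leave consent withdrawal, the noncompliance triggers in 5.7 and the safety provisions as they are (positive pregnancy test before a scan in 2.7, removal for pregnancy in 5.4.2, the Medical Monitor's authority in 5.13). This concerns data collection and analysis only, not care.

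**Section 2.18.**
1. Analyse patients in the assigned arm with all available visits, for example by a mixed model, in place of complete-case paired tests and repeated-measures ANOVA.
2. Report missing visits with reasons, by arm.
3. Add a sensitivity analysis that ranks patients lost after failure as worst. It addresses loss that depends on unrecorded outcomes, which the mixed model does not correct.
4. Record the date of any later revision surgery (section 1.1 leaves it open). Analyse outcomes after it as observed, with the same sensitivity analysis.

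**Cost.** Wording in two sections, slightly more analysis work and a few retained visits. A patient whose failure is seen at month 6 would keep the scans at months 12 and 24: 2 × 1.3 = 2.6 rem by CT, within the 5.2 rem total in section 5.1 (4 × 1.3). No procedure is added.

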5.10 Question has been moved to 5.17

5.11 Question has been moved to 5.16

[reviewer notes-]

Section 5 - Potential Risks and Benefits of Study Participation

5.12 Does participation in this research study offer the potential for direct benefit to the research subjects? Yes - Describe the direct benefit that subjects may receive as a result of study participation. Indicate if all, or only certain, of the subjects may derive this potential benefit. Describe the benefit: Fat grafting procedures performed for clinical purposes have been associated with positive results in improving the appearance of patients; it is also anticipated to improve pain related to inadequate soft tissue coverage. In this case, subjects are likely to have a visible improvement in their limb deformities, with the potential of improved prosthetic fit and comfort, resulting in improved mobility. Additionally, these improvements may have a positive impact on quality of life, as assessed by the instruments used in this study. Although we can not guarantee a positive outcome from this research fat grafting procedure, there may be a direct benefit to the research subject from his/her participation in this research study. In addition, this research may provide a greater understanding of the effects of fat grafting over time.

5.13 Describe the data and safety monitoring plan associated with this study. If the research study involves multiple sites, the plan must address both a local and central review process. Data Safety Monitoring Plan The Data Safety and Monitoring Plan for this trial will consist of two parts. A Local Data and Safety Monitoring Plan will be implemented by the Principal Investigator to ensure that there are no changes in the risk/benefit ratio during the course of the study and that confidentiality of research data is maintained. This DSMB will consist of the PI, Co-Investigators and study personnel who will meet and discuss monthly the study (e.g., study goals and modifications of those goals; subject recruitment and retention; progress in data coding and analysis; documentation, identification of adverse events or research subject complaints; violations of confidentiality) and address

any issues or concerns at that time. Minutes will be kept for these meetings and will be maintained in the study DSMB binder. Any instances of adverse events will be reported immediately to the University of Pittsburgh IRB in accordance with the guidance on the IRB website. The annual IRB renewal for this study will include a summary report of the Data and Safety Monitoring Plan findings from the study for the prior year. We will include the following information at the time of the IRB renewal regarding the frequency of the monitoring, the dates that the monthly meetings took place, a summary of the cumulative adverse events, external factors or relevant information that might have an impact on the safety or ethics of the study, and final conclusions regarding changes to the anticipated risk/benefit ratio to study participation and final recommendations related to the continuation, changing, or termination of the study. The protocol will be not be initiated until written notification of approval of the research project is issued by the HRPO. A copy of the approved continuing review report and the local IRB approval notification will be submitted to the USAMRMC ORP HRPO as soon as these documents become available. A copy of the approved final study report and local IRB approval notification will be submitted to the USAMRMC ORP HRPO as soon as these documents become available. Substantive modifications to the research protocol and any modifications that could potentially increase risk to subjects must be submitted to the HRPO for approval prior to implementation. The USAMRMC ORP HRPO defines a substantive modification as a change in Principal Investigator, change or addition of an institution, elimination or alteration of the consent process, change to the study population that has regulatory implications (e.g. adding children, adding active duty population, etc.), significant change in study design (i.e. would prompt additional scientific review), or a change that could potentially increase risks to subjects. All other amendments must be submitted with the continuing review report. All unanticipated problems involving risk to subjects or others must be promptly reported by [contact]), by email ([contact]), or by [contact]) to the HRPO. A complete written report will follow the initial notification. In addition to the methods above, the complete report can be sent to the US Army Medical Research and Materiel Command, ATTN: MCMR-RP, [name] Suspensions, clinical holds (voluntary or involuntary), or terminations of this research by the IRB, the institution, the sponsor, or regulatory agencies will be promptly reported to the USAMRMC ORP HRPO. A copy of the continuing review report and the re-approval notification by the UP IRB must be submitted to the HRPO as soon as possible after receipt of approval. Please note that the HRPO also conducts random audits at the time of continuing review and additional information and documentation may be requested at that time. The final study report submitted to the UP IRB, including a copy of any acknowledgement documentation and any supporting documents must be submitted to the HRPO as soon as all documents become available. The knowledge of any pending compliance inspection/visit by the Food and Drug Administration (FDA), Office for Human Research Protections, or other government agency concerning this research; the issuance of inspection reports, FDA Form 483, warning letters, or actions taken by any regulatory agencies including legal or medical

actions; and any instances of serious or continuing noncompliance with the regulations or requirements must be reported immediately to the HRPO. Accurate and complete study records will be maintained and made available to representatives of the USAMRMC as a part of their responsibility to protect human subjects in research. All research records are stored in a confidential manner so as to protect the confidentiality of subject information. Per DoD Directive 3216.02, all greater than minimal risk studies require a Medical Monitor. The USAMRMC ORP HRPO also reserves the authority to require assignment of a Medical Monitor for those protocols assessed as presenting no greater than minimal risk to the subjects participating in the study. The second part of the DSMP will be the inclusion of an Independent Data Safety Monitoring Board (IDSMB). This IDSMB will convene once a year or as needed for review of all unanticipated events, adverse events, and serious adverse events affecting the risk to the human subject or others. The members of the IDSMB include Drs. [name] and [name] who are all present faculty members within the Department of Plastic Surgery at the University of Pittsburgh, without any involvement in this research protocol, they are not under the supervision of the PI or have a conflict of interest. [name], a member of the Independent Data Safety and Monitoring Board (IDSMB) will act as the Research Monitor for this study; he is available on site to respond to any urgent or emergency situations that may arise during the study and to serve as the subject advocate. The Research Monitor is required to review all unanticipated problems involving risk to subjects or others, serious adverse events and all subject deaths associated with the protocol and provide an unbiased written report of the event. At a minimum, the Research Monitor must comment on the outcomes of the event or problem and in case of a serious adverse event or death, comment on the relationship to participation in the study. The Research Monitor must also indicate whether he/she concurs with the details of the report provided by the principal investigator. The Medical Monitor has the authority to stop the research at any time; he /she can remove individuals from the study, and take any steps necessary to protect the safety and well being of participants until the IRB has time to assess the study. This IDSMB will evaluate any adverse events and research staff adherence to subject confidentiality and de-identification processes. The IDSMB members will discuss, if necessary, any changes to the risk/benefit ratio of this study for the PI's report to the local IRB of all reporting adverse events, external factors or relevant information that might have an impact on the safety or ethics of the study, and final conclusions regarding changes to the anticipated risk/benefit ratio to study participation and final recommendations related to the continuation, changing, or termination of the study as outlined by the University of Pittsburgh IRB.

[reviewer notes-]

Section 5 - Potential Risks and Benefits of Study Participation

- 5.14 What precautions will be used to ensure subject privacy is respected? (e.g. the research intervention will be conducted in a private room; the collection of sensitive information about subjects is limited to the amount necessary to achieve the aims of the research, so that no unneeded sensitive information is being collected, drapes or other barriers will be used for subjects who are required to disrobe)

All aspects of the study will be performed in a private room, including the consenting process, exams, urine pregnancy testing, questionnaires, photographs, CT scan, laboratory blood draw and the fat grafting procedure. The collection of sensitive information about subjects is limited to the amount necessary to achieve the aims of the research, so that no unneeded sensitive information is being collected, drapes or other barriers will be used for subjects who are required to disrobe.

- 5.15 What precautions will be used to maintain the confidentiality of identifiable information? (e.g., paper-based records will be kept in a secure location and only be accessible to personnel involved in the study, computer-based files will only be made available to personnel involved in the study through the use of access privileges and passwords, prior to access to any study-related information, personnel will be required to sign statements agreeing to protect the security and confidentiality of identifiable information, whenever feasible, identifiers will be removed from study-related information, precautions are in place to ensure the data is secure by using passwords and encryption, because the research involves web-based surveys, audio and/or video recordings of subjects will be transcribed and then destroyed to eliminate audible identification of subjects)

Participation in this research study does involve the potential risks of a breach of confidentiality of the medical record information and associated privacy of the participants. The study investigators will take steps to reduce these risks by: 1) removing direct participant identifiers (i.e., names, social security numbers, medical record numbers) from information stored in the study records; 2) securing, in a separate location, and limiting access to information linking codes assigned to the study record information with direct participant identifiers; and 3) limiting access to information contained within the study records to study investigators only. Paper-based records will be kept in a secure location and only be accessible to personnel involved in the study, computer-based files will only be made available to personnel involved in the study through the use of access privileges and passwords, prior to access to any study-related information, whenever feasible, identifiers will be removed from study-related information, precautions are in place to ensure the data is secure by using password restricted and folder level access by permission only on UPMC servers. Reference to sample: All research samples will be stored to include assigned code numbers, and any information linking these code numbers to the corresponding subjects' identities will be kept in a separate, secure location located in the security manned Biomedical Science Tower at the University of Pittsburgh. Should the subject decide to withdraw or be withdrawn from study participation, the already collected samples will then be rendered anonymous, i.e., the link between the code and the identity will be destroyed.

If the subject requests that the samples be destroyed and the link to the samples has not yet been rendered anonymous, we will destroy the samples. However if link to the samples were already rendered anonymous prior to the subject's request, we will not be able to identify the subject's samples making it impossible to destroy them. It is the Principal Investigator's intention to make subject de-identified information available to secondary investigators after all research study testing has been completed. These associated subject information will not include subject identifiers. The photographs will be housed as electronic files within the Canfield camera system. The system is password protected and is located within the locked offices of the Aesthetic Plastic Surgery Center located at [name]. While the photographs will be labeled with an ID code, there is a risk of loss of confidentiality. Digital recording (i.e. photography or video) are being collected from any and all portions of the subject's pre-operative, operative, and post-operative course of treatment. These may include, but not be limited to, videos of personal interviews, functional assessment testing and clinical exams or photos of follow up clinical course, biopsies, etc. and will be de-identified and stored indefinitely in a secure password protected location on the UPMC server. These digital recordings and/or photos may be used for medical education and training, publication, and media reports – and, in any mode of transmission, including and not limited to: print, e-mail, television, internet, etc. While photograph will be de-identified, video recordings will remain identifiable. Regarding the use of these digital recordings for education, training, publication and storage purposes, the subject will not be identified by name, only by a unique code number. The subject's identifiable features in these photographs will be blacked out (i.e., eyes, facial features, etc.). Regarding the use of the subjects digital recordings for media purposes, the subject may be identified by name, but permission from the subject will be obtained in a separate consent document prior to the recordings being obtained (Media consent). The subjects are not required to give this permission and can refuse at any time after giving consent to these digital recordings being obtained and can still participate in this study without permitting these recordings. All data entered on TrialSpark as part of the registration process (e.g., email address, personal information) is subject to TrialSpark's extensive security protocol. Study-specific information, including data acquired during the study, may be accessed by engineers on an as needed basis to troubleshoot a technical issue (duplicate registrations, error in date entry format). TrialSpark maintains a protective privacy policy in reference to e-mail addresses, personal information, and any additional data entered on TrialSpark. TrialSpark does not sell or make available specific information about clients or their data with third-parties. The Secure Socket Layer (SSL) software, which encrypts all inputted information, keeps the information private. TrialSpark backend servers are stored at secure data centers. TrialSpark complies with the U.S. and E.U. Safe Harbor Framework and the U.S. and Swiss Safe Harbor Framework, expounded upon by the U.S. Department of Commerce. Further, TrialSpark complies with the Safe Harbor Privacy Principles of notice, choice, onward transfer, security, data integrity, access, and enforcement. All of the information collected is stored in a HIPAA compliant database with additional encryption, virtual, and physical safeguards. Data is encrypted at transfer and at rest.

- 5.16 If the subject withdraws from the study, describe what, if anything, will happen to the subject's research data or biological specimens.

Any identifiable research or medical information recorded for, or resulting from, a subject's participation in this research study prior to the date that the subject formally withdrew his/her consent will continue to be used and disclosed by the investigators for the purposes described above. All research samples will be stored to include assigned code numbers, and any information linking these code numbers to the corresponding subjects' identities will be kept in a separate, secure location located in the Department of Plastic Surgery at the University of Pittsburgh. Should the subject decide to withdraw or be withdrawn from study participation, the already collected samples and all digital recordings will be kept and will be rendered anonymous, i.e., the link between the code and the identity will be destroyed. If the subject requests that the samples be destroyed and the link to the samples has not yet been rendered anonymous, we will destroy the samples. However if link to the samples were already rendered anonymous prior to the subject's request, we will not be able to identify the subject's samples making it impossible to destroy them. All samples and digital recordings collected during their participation in this clinical trial, upon their early withdraw from the study, will be kept and not destroyed, but processed specifically as outlined in the research design for this trial. Upon the subject's withdrawal from the study, should they specifically request that their biological samples collected for research purposes be destroyed, we will stop all testing and destroy any remaining unprocessed samples. It is the Principal Investigator's intention to make subject de-identified information available to secondary investigators after all research study testing has been completed. These associated subject information will not include subject identifiers. Subjects will be instructed that they may choose to withdraw from this study at any time, but it is important that they continue to be monitored by a physician after they receive the research Fat grafting procedure in order to ensure their safety. It is also important for the subject to contact study personnel if they later experience any side effects that they might feel are related to the research study.

